- ❖ **Secondary Objective 2b:** Evaluate the treatment outcomes (HbA1c and hypoglycemic events) and prescriber behavior (observed TDD in claims and prescribed TDD from the physician) among T2DM patients before and after U-500R syringe initiation and U-500R Kwikpen initiation separately, as well as before and after U-500R device switch from syringe to Kwikpen in a subset of T2DM patients who had information on HbA1c, prescribed TDD by a physician, and had observed TDD information available in the claim:
- Determine how, in each cohort, the observed TDD in claims differs from the physician-prescribed TDD.
 - Determine, in each cohort, the dynamics between observed TDD in claims, physician-prescribed TDD, and treatment outcomes (HbA1c and hypoglycemic events).

Research Objective 3: Health Care Costs

- ❖ **Primary Objective 3:** Evaluate out-of-pocket costs and total health care costs among T2DM patients before and after U-500R syringe initiation and U-500R Kwikpen initiation separately:
- Evaluate and characterize the dynamic relationship between observed TDD in claims, insulin adherence, and out-of-pocket costs.
 - Evaluate and characterize the dynamic relationship between observed TDD in claims, insulin adherence, and total health care costs.

5. Research Design

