Mediation analysis following the Baron and Kenny's steps will be considered to understand the impact of index event (time: pre-index indicates use of othe insulin and post-index indicates U-500R use) on HbA1c through potential mediators. Adherence is considered as a potential mediator between the HbA1c and time. The key steps in mediation analysis include a model of the mediator (adherence) as a function of the predictor (time) and a model of the outcome (HbA1c) as a function of both the mediator (adherence) and the predictor (time). Bootstrapping method will be used to test the effect of mediator. The detailed steps are described below:

Step 1: Effect of predictor (time) on the outcome (HbA1c):

In the first step, the effect of time on the dependent variable HbA1c will be assessed. Statistically, a significant relationship between the two variables will trigger the next step of the mediation analysis. However, it is suggested that the clinical significance and theoretical evidence should be considered in the case of failure to detect an association that is statistically significant. Since the effect of time on HbA1c is the primary interest of this analysis, we will carry out the next step regardless of the significance between time and HbA1c.

Step 2: Effect of predictor (time) on the mediator (adherence):

The effect of time (predictor) on the hypothesized mediator adherence will be assessed, and adherence will be considered as a dependent variable in the model. Potential mediation effect will be supported by a statistically significant relationship between time and adherence, which will lead to the next step of the analysis.

Step 3: Combined effect of predictor (time) and mediator (adherence) on the outcome (HbA1c):

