a longitudinal feature in which a continuous outcome variable is measured for the same subject repeatedly over the time period. Based on the distribution of the data, observations measured for the same subject are likely to be correlated over the study period and these data are considered as “multilevel” data. In addition, mixed linear model has a mixed effect consisting both fixed and random effects. For this objective, mixed linear model helps to evaluate the effect of both time varying and time-independent variables on the costs, while taking into account for correlation due to multiple assessments from the same individual. In the current model, costs which are measured at two time intervals (before and after the index event; U-500R initiation), will be considered the dependent variable. Observed TDD will be considered as the time varying covariates in the model (measured both before and after the index date), and the time-independent covariates will include the demographic and clinical characteristics.

The complete list of covariates will include:

- age
- sex
- region
- baseline CCI score
- observed TDD from claims
- Medicare (yes/no)
- time (pre/post)

Note: For all the multivariate analyses the covariates will be included as per the availability in each of the VHA, Truven claims, linked Truven claims and EMR data and pooled VHA and linked Truven data. Age, sex, region, medicare (yes/no), and CCI score will be assessed during pre-index period. Observed TDD will be calculated during the entire pre-index and post-index periods, respectively.

Adherence will not be included as one of the covariates here due to the high collinearity between time and adherence. Hence, further mediation analysis will be performed to determine the mediator effect of adherence on costs.

Mediation Analysis:

Mediation analysis following the Baron and Kenny’s steps will be considered to understand the impact of index event (time) on costs through potential mediators. Adherence is considered as a potential mediator between the costs and time. The key steps in mediation analysis include a model of the mediator (adherence) as a function of the predictor (time) and a model of the outcome (costs) as a function of both the mediator (adherence) and the predictor (time). Bootstrapping method will be used to test the effect of mediator. The detailed steps are described below:

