[2018-7241 Study Identifier] Observational Study Protocol*Step 1: Effect of predictor (time) on the outcome (costs):*

In the first, the effect of time on the dependent variable costs will be assessed. Statistically, a significant relationship between the two variables will trigger the next step of the mediation analysis. However, it is suggested that the clinical significance and theoretical evidence should be considered in the case of failure to detect an association that is statistically significant. Since the effect of time on costs is the primary interest of this analysis, we will carry out the next step regardless of the significance between time and costs.

Step 2: Effect of predictor (time) on the mediator (adherence):

The effect of time (predictor) on the hypothesized mediator adherence will be assessed, and adherence will be considered as a dependent variable in the model. Potential mediation effect will be supported by a statistically significant relationship between time and adherence, which will lead to the next step of the analysis.

Step 3: Combined effect of predictor (time) and mediator (adherence) on the outcome (costs):

Adherence will be included and adjusted as a covariate in the model assessing the relationship between time (predictor) and the dependent variable costs. Evidence of a mediation effect will be strengthened if the relationship between time and costs disappears or weakens while adjusting for adherence. If the effect of time on costs became insignificant, this indicates that the relationship between time and costs is fully mediated by adherence (full mediation); and if the relationship remains significant with a reduced magnitude, this indicates that adherence is partially mediating the relationship between time and costs (partial mediation). If any of the mediation effect exists, the next step will be used to further test the significance of the mediation effect.

Step 4: Assess the statistical significance of the effect of the mediator (adherence):

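### The only cost model that contains adherence appears to depend on a significant pre/post change in mean adherence, so the adherence part of Primary Objective 3 may go unestimated

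*Protocol*

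**What the plan says.** Protocol section 4.1, Primary Objective 3, has two sub-aims: "Evaluate and characterize the dynamic relationship between observed TDD in claims, insulin adherence, and out-of-pocket costs" and "Evaluate and characterize the dynamic relationship between observed TDD in claims, insulin adherence, and total health care costs".

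Section 6.4.1, Primary Objective 3, specifies a generalized linear mixed model for costs with observed TDD and time among its covariates. On adherence it says: "Adherence will not be included as one of the covariates here due to the high collinearity between time and adherence". It then defers the matter: "Hence, further mediation analysis will be performed to determine the mediator effect of adherence on costs".

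The mediation analysis has four steps.

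- **Step 1** (time on costs) first treats significance as the trigger for continuing, then sets that aside: "we will carry out the next step regardless of the significance between time and costs".
- **Step 2** (time on adherence) says mediation will be "supported by a statistically significant relationship between time and adherence, which will lead to the next step of the analysis". It has no corresponding waiver.
- **Step 3** is where adherence enters a cost model: "Adherence will be included and adjusted as a covariate in the model assessing the relationship between time (predictor) and the dependent variable costs". It closes by making the bootstrap conditional on some mediation effect having been seen.
- **Step 4** is the bootstrap test of the indirect effect.

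The HbA1c mediation under Primary Objective 2 has the same structure, and its Step 2 begins identically: "Potential mediation effect will be supported by a statistically significant relationship between time and adherence".

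**The concern.** The time variable has two levels, pre and post, so Step 2 tests whether mean adherence shifts between the periods. The sub-aims ask how costs vary with adherence. Some patients can become more adherent and others less, which leaves the mean flat while giving real information on how costs move with adherence. A null Step 2 is a good reason not to claim mediation, but it is no reason to leave out the adherence coefficient.

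Two things are at stake. With a stable mean, the adherence part of a primary objective has no estimate. And whether that estimate appears at all would turn on cohort size and a significance test of something else, not on the adherence-cost relationship.

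**Working it through.** **1. Where adherence and costs could meet (section 6.4.1)**

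| Planned analysis | Adherence | Costs | Conditional? |
|---|---|---|---|
| Objective 1 mixed model | outcome | no | no |
| Objective 3 descriptives | no | pre vs post | no |
| Objective 3 cost model | excluded | outcome | no |
| Mediation Step 1 | no | outcome | no |
| Mediation Step 2 | outcome | no | no (Step 1 waived) |
| Mediation Step 3 | covariate | outcome | on Step 2, as most naturally read |
| Mediation Step 4 | mediator | outcome | on Step 3 showing mediation |

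Only Steps 3 and 4 hold both quantities, and both are conditional.

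**2. How often Step 2 would pass**

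The protocol states no figure to reproduce. Table 4 gives VHA counts only, whereas Objective 3 uses the MarketScan claims database, and no spread of the proportion of days covered (PDC) is given. The two-sided 0.05 level is from section 6.3. Assumed here: SD of within-patient PDC change 0.25; n = 300 or 1000.

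For a true mean shift d, with z = d·√n / SD, P(pass) = Φ(z − 1.96) + Φ(−z − 1.96).

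At n = 300, SD/√n = 0.25/17.32 = 0.01443:

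- d = 0: Φ(−1.96) + Φ(−1.96) = 5%
- d = 0.02: z = 1.386; Φ(−0.574) plus a negligible tail = 28%
- d = 0.05: z = 3.464; Φ(1.504) = about 93%

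At n = 1000, SD/√n = 0.00791:

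- d = 0: 5%
- d = 0.02: z = 2.530; Φ(0.570) = 72%
- d = 0.05: about 100%

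Sensitivity to the SD: at d = 0.02 and n = 1000, the pass rate is 89% with SD 0.2, 56% with 0.3 and 35% with 0.4. At d = 0.05 and n = 300, it is 99%, 82% and 58%.

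**3. Whether the same data could inform the adherence-cost slope**

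This is an illustration only. Assume a within-patient slope of −0.5 log-cost per unit PDC and an SD of log-cost change of 1.0. Then SE = 1.0/(0.25·√n), and power ≈ Φ(0.5/SE − 1.96).

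- n = 300: SE = 0.231; Φ(0.205) = 58%
- n = 1000: SE = 0.126; Φ(1.99) = 98%

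This power does not depend on d, so a flat mean does not remove the information.

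**4. The collinearity reason**

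With equal numbers of pre and post observations and within-period PDC SD s, the correlation of time with PDC is r = (d/2)/√(s² + d²/4), and VIF = 1/(1 − r²).

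- d = 0: r = 0, VIF = 1.00
- d = 0.10, s = 0.2: r = 0.243, VIF = 1.06
- d = 0.10, s = 0.3: r = 0.164, VIF = 1.03

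When mean adherence is stable, the stated reason for excluding adherence from the cost model vanishes, and that is also when Step 2 is likely to fail.

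**The case against.** **The stop is not written down.** No sentence says the analysis ends after a null Step 2, and the introduction to the mediation analysis describes the cost model with adherence, and the bootstrap, without conditions. This stands in part. A reader might infer an explicit stopping rule, but the text supports only an implied one. The implication is still the natural reading: the authors waived the condition in Step 1 and not in Step 2, and the introduction hands over to the detailed steps. If the other reading was meant, the text still needs to say so.

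**Step 2 is a proper part of the Baron and Kenny sequence.** True, and it stands as a rule for interpreting mediation. It does not justify withholding an association that the objective separately asks for.

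**The objective is still largely met.** This also stands. A reader might infer that Primary Objective 3 as a whole goes unanswered. It does not: the before/after cost comparison and the TDD-cost association are estimated unconditionally. Only the adherence element of the two sub-aims is exposed.

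**The authors expect a marked shift.** Citing high collinearity between time and adherence suggests this, and a shift of 0.05 would usually pass. A reader might take from the zero-shift figure that the answer is lost 95% of the time. That holds only for a mean shift of exactly zero, which the documents give no reason to presume. Equally, a large shift is an expectation, not a result.

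**The slope power does not describe Step 3.** Correct. The planned mixed model would generally blend within- and between-patient information, so the 58% and 98% only illustrate that information exists.

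**Conclusion.** The concern holds in limited form. As most naturally read, the sequence makes the only cost model containing adherence conditional on a significant change in mean adherence, a test that does not bear on the adherence-cost relationship. If that test is null, the adherence part of Primary Objective 3 would not be estimated.

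The likelihood cannot be fixed from the protocol. It ranges from near-certain omission if the mean does not move to a small risk if the shift is 0.05 or more in a cohort of several hundred with a PDC-change SD of about 0.25. Cohort size, PDC spread and PDC shift are all assumptions here.

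The HbA1c mediation carries the same wording, but the case there is weaker: that objective asks whether adherence contributed to changes in HbA1c, which is closer to a mediation question, so Step 2 bears on it more directly. The change is worth making because it is cheap and removes an avoidable gap in a primary objective.

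**What to change.** In section 6.4.1, Primary Objective 3, Mediation Analysis:

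- **Step 2:** state that the Step 3 model will be fitted whatever the significance of Step 2, and that Step 2 serves only to interpret mediation.
- **Step 3:** state that the adherence coefficient, with its 95% CI, will be reported for both total and out-of-pocket costs as the answer to the adherence part of the objective.
- **End of Step 3:** remove the condition that a mediation effect must be seen first, so that the Step 4 bootstrap of the indirect effect is always run. Waiving Step 2 alone would leave this second condition in place.

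Align the matching Steps 2 and 3 in the HbA1c mediation for consistency.

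The cost is a few sentences in each mediation section. The models are already specified and no new data are needed.

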Observed average daily dose (ADD) in claims	Truven: Outpatient pharmacy claims table VHA: Pharmacy file	
The observed insulin ADD will be calculated both in the pre-and post-index periods among the U-500R syringe initiators, U-500 Kwikpen initiators, and the U-500R device switchers. ADD will be reported both as continuous and categorical variable.
 
Pre-index ADD: total number of insulin units/ the total number of days in the pre-index period.
 
Post-index ADD: total number of insulin units/ the total number of days in the post-index period.
 
Additionally the ADD of U-500R syringe only and the U-500R Kwikpen only will be reported in the U-500R syringe initiators and Kwikpen initiators respectively.
 
Note: Total insulin units calculation in based on the similar approach as described in TDD.

Adherence	Truven: Outpatient pharmacy claims table VHA: Pharmacy file	
Adherence to insulin will be assessed using the proportion of days covered (PDC), and reported in categories of 0-20%, 20-40%, 40-60%, 60-80%, and 80%-100%. PDC will be calculated both in the pre-and post-index periods among the U-500R syringe initiators, U-500 Kwikpen initiators ,and the U-500R device switchers.
 
For U-500R syringe initiators (index event 1a):

[2018-7241 Study Identifier] Observational Study Protocol

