		
PDC before U-500R initiation will be calculated as the number of days covered by the prescription claims of insulin (any insulin)/total days in the pre-index period;
 
PDC after U-500R initiation will be calculated as the number of days covered by the prescription claims of insulin (any insulin)/total days in the post-index period.
 
For U-500R Kwikpen initiators (index event 1b):
 
PDC before U-500R initiation will be calculated as the number of days covered by the prescription claims of insulin (any insulin)/total days in the pre-index period;
 
PDC after U-500R initiation will be calculated as the number of days covered by the prescription claims of insulin (any insulin)/total days in the post-index period.
 
For U-500R device switchers (index event 2):
 
PDC before switching will be defined as the number of days covered by the prescription claims of insulin (U-500R syringe)/total days in the pre-index period;
 
PDC after switching will be defined as the number of days covered by the prescription claims of insulin (U-500R Kwikpen)/total days in the post index period
 
Note: For the calculation of PDC in patients with evidence of a basal-bolus regimen, basal/bolus-premixed, or basal/bolus-U-500R, the overlap days will be adjusted for the concomitant use of basal and bolus insulins, but will not be adjusted within basal and within bolus insulins.

--	--	---

[2018-7241 Study Identifier] Observational Study Protocol

Persistence/time to discontinuation	Truven: Outpatient pharmacy claims table VHA: Pharmacy file	Persistence will be defined as the percentage of patients continuing on the index medication in the post-index period. Patient is considered to discontinue if there is no refill of the index medication within 60 days from the run-out date (date of last prescription + days of supply) i.e, a gap of >60 days from the run out date. The run-out date will be the discontinuation date. Time to discontinuation will be defined as the total number of days from the index date to the discontinuation date during the post-index period.
Abandonment/fill rates	Truven: Outpatient pharmacy claims table VHA: Pharmacy file	The average number of insulin prescription fills will be calculated in the pre- and post-index periods among all the study cohorts.

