All-cause health care total and out-of-pocket costs	Truven: Inpatient service table, outpatient service table, outpatient pharmacy claims table	All-cause health care costs for total and out-of-pocket costs including inpatient costs, outpatient costs, pharmacy costs, total costs (inpatient + outpatient + pharmacy), out-of-pocket inpatient costs, out-of-pocket outpatient costs, out-of-pocket pharmacy costs and total out-of-pocket costs (inpatient + outpatient + pharmacy) will be computed among T2DM patients before and after U-500R syringe initiation and U-500R Kwikpen initiation. Costs will be adjusted to 2018 US dollars using the annual medical care and drug costs components of the Consumer Price Index (CPI) to reflect inflation.
---	---	--

Note: When comparing the TDD, ADD, adherence, fill rates and claim gaps in the pre vs post-index periods among the U-500R device switchers, only the claims corresponding to U-500R (syringe in the pre-index and Kwikpen in the post-index) will be considered. To be more specific we will be looking only at the treatment patterns of U-500R alone rather than the regimen.

However, for the U-500R initiators, the regimen use (use of different types of insulin) in the pre-index period will be compared to the regimen use (U-500R + other insulins) in the post-index period.

[2018-7241 Study Identifier] Observational Study Protocol**6. Sample Size and Statistical Methods****6.1 Determination of Sample Size**

The preliminary sample sizes for the VHA databases from 2013-2018 are shown below. This study will use the most recently available 5 years of data.

Table 4. Preliminary Sample Size

Database	Counts
VHA (01APRIL2013-31MARCH2018)	
T2DM (ICD-9: 250.x0, 250.x2) + Humulin R U-500 Kwikpen (NDC: 00002882427, 00002882459)	4,120
≥2 HbA1c measurements	4,066
T2DM + Humulin R U-500 Vial (NDC: 00002850101)	5,863
≥2 HbA1c measurements	5,718

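### PDC in the cost mediation ignores hospital stays: a stay that delays a refill lowers PDC and raises cost together, so Step 3 can misread admissions as an adherence effect

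*Protocol*

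**What the plan says.** Section 5.5, Table 3 (Adherence) defines PDC for the initiator cohorts before the index date as "the number of days covered by the prescription claims of insulin (any insulin)/total days in the pre-index period" and afterwards as "the number of days covered by the prescription claims of insulin (any insulin)/total days in the post-index period". The source is given as "Truven: Outpatient pharmacy claims table VHA: Pharmacy file". Table 1 assigns Primary Objective 3 to the Truven MarketScan claims alone, so the numerator there holds outpatient fills only. One adjustment to covered days is described: "overlap days will be adjusted for the concomitant use of basal and bolus insulins, but will not be adjusted within basal and within bolus insulins". Nothing is said about days in hospital.

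Table 3 (All-cause health care total and out-of-pocket costs) puts inpatient cost into both outcomes: "total costs (inpatient + outpatient + pharmacy" and "total out-of-pocket costs (inpatient + outpatient + pharmacy".

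Section 6.4.1 (Primary Objective 3) lists the complete covariates of the cost model: age, sex, region, baseline CCI, observed TDD, Medicare status and time. Step 3 of the mediation then adds PDC: "Adherence will be included and adjusted as a covariate in the model assessing the relationship between time (predictor) and the dependent variable costs". Step 4 bootstraps the indirect effect and reports a percentage mediated.

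**The concern.** While a patient is in hospital, the hospital may supply the insulin and the home supply may go unused. If so, the next outpatient fill comes later and measured PDC falls, although the patient missed nothing. The same days generate inpatient cost in the same 9-month window. Baseline CCI cannot remove a link that arises within the window, and no term in the model represents admissions or inpatient days.

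At stake is the adherence coefficient in Step 3 and whatever is built on it. Objective 3 asks for the relationship between adherence and costs in its own right. The protocol also treats a significant indirect effect as clear evidence of mediation. An association produced by admissions could be reported as adherence acting on costs.

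**Working it through.** The protocol gives no effect size, power or sample size for this mediation, so there is no figure of its own to reproduce.

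**Inputs from the protocol.** The PDC rule and its source, the cost components, the covariate list, and two 9-month periods (9/12 × 365.25 ≈ 274 days each).

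**Assumed inputs, not in the protocol.** 0.2 to 0.5 admissions per 9 months; mean stay 5 to 12 days; $3,000 per inpatient day; fills of 30 or 90 days; other cost with median $8,000.

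**Step 1: ceiling on the PDC loss.** Maximum loss = inpatient days / 274. For 3 days this is 1.1 points; 5 days, 1.8; 10 days, 3.6; 20 days, 7.3. The loss is nil if an outpatient fill spans the stay and the next refill is on time.

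**Step 2: spurious slope with no true adherence effect.** There were 6,000 simulated patients per scenario, one period each, with true adherence independent of cost. Total cost = other cost + $3,000 × inpatient days, regressed on PDC in a gamma model with log link, without the plan's random effect or covariates.

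- Refills on schedule: correlation of PDC with inpatient days -0.02 to +0.02; cost change per +10 PDC points -1.4% to +1.5% (SE 0.9 to 1.3). There is no artefact.
- Home supply saved during the stay (cost change per +10 PDC points, SE in brackets):

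| Fill | Admissions | Mean stay | PDC as defined | Inpatient days removed only | Removed and supply carried forward |
|---|---|---|---|---|---|
| 30 d | 0.2 | 5 d | -1.5% (1.0) | -0.9% (1.0) | +2.2% (1.0) |
| 30 d | 0.5 | 6 d | -9.0% (1.1) | -6.4% (1.1) | +1.1% (1.1) |
| 30 d | 0.5 | 12 d | -21.5% (1.2) | -12.3% (1.3) | +1.2% (1.3) |
| 90 d | 0.2 | 5 d | -2.2% (0.9) | -2.2% (0.9) | +0.1% (0.9) |
| 90 d | 0.5 | 6 d | -6.2% (1.0) | -5.9% (1.0) | +1.1% (1.0) |
| 90 d | 0.5 | 12 d | -15.3% (1.1) | -13.1% (1.1) | +2.3% (1.2) |

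Removing inpatient days alone leaves more than half of the artefact in every row. Carrying the supply forward as well brings the slope close to zero.

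**Step 3: second simulation at moderate admission levels.** With 0.3 stays of 5 to 8 days, the slope for PDC as defined was about 0% with refills on schedule and -1.4% to -5.7% with supply saved. The adjusted PDC gave +0.8% and -0.3% with supply saved, but +2.0% to +3.7% with refills on schedule, because the carried supply then fills later gaps that were real.

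**Step 4: net sign.** Insulin fills raise PDC and pharmacy cost together. Take $12,000 other cost, 0.3 stays of 5 days and $3,000 per day. Mean cost = 12,000 + 0.3 × 5 × 3,000 = $16,500. A simulation on these inputs, with every inpatient day delaying the refill, gave -2.3% per 10 points: 0.023 × 16,500 ≈ $380 per 27.4 covered days. Insulin cost above 380 / 27.4 ≈ $14 per covered day would reverse the sign. With 8-day stays, mean cost is $19,200 and the slope -5.1%: 0.051 × 19,200 ≈ $979, and 979 / 27.4 ≈ $36. When an assumed $40 per covered day was added to the Step 2 simulation (30-day fills, supply saved), the slope was +3.5% at the lowest admission level and -14.6% at the highest. In the Step 3 simulation it was +0.2% to +3.7%.

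**Step 5: passage into the indirect effect.** On the log scale, indirect effect = (change in PDC between periods) × (PDC slope). With a slope of -9.0% per 10 points and an assumed 5-point change in PDC, this is 0.5 × ln(0.910) = -0.047, or -4.6% of cost. With no change in PDC it is zero.

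**The case against.** A reader might infer that the protocol scores hospital days as days without insulin, so that the association arises by construction and always favours the conclusion that better adherence lowers costs. The documents do not support this. Table 3 counts days covered by claims, so a hospital day spanned by an outpatient fill is covered. With refills on schedule the artefact vanishes. Pharmacy cost pulls in the opposite direction. All three points stand.

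The simulations also do not give error rates for the planned test. They address the Step 3 slope in simplified models, not the bootstrapped indirect effect, and they cover total cost only. The size for out-of-pocket cost is unknown. This stands too.

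It can be argued that the handling of inpatient days belongs in an analysis plan or program, and that Section 5.2 already admits that a filled prescription does not show consumption. This stands only in part. The protocol fixes the numerator, the denominator, the one adjustment and a complete covariate list, and its limitations do not mention this mechanism.

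The strongest objection is that the adjusted PDC assumes supply was saved, and creates an opposite artefact where it was not. That is correct. It rules out simply replacing the stated definition.

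**Conclusion.** The concern holds as a conditional one. The protocol's PDC, cost outcome and covariate list leave Step 3 open to reading admissions as an adherence effect whenever stays delay refills. On assumed inputs, the distortion runs from nil (refills on schedule) to about -1.5% to -21.5% of cost per 10 PDC points (supply saved, from few short stays to more frequent long ones), before pharmacy cost is counted. Two opposing links do not cancel into an interpretable coefficient, and the net sign cannot be told in advance. The indirect effect and percentage mediated are affected only if PDC also differs between the pre- and post-index periods; the adherence coefficient can be affected regardless. The HbA1c mediation uses the same PDC but its outcome contains no inpatient cost, so this link does not apply there.

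**What to change.** Keep the PDC of Table 3 and repeat Steps 2 to 4 of the Objective 3 mediation with an inpatient-adjusted PDC. This version removes inpatient days (admission to discharge) from numerator and denominator, and carries supply unused during the stay past discharge. Both parts are needed. Take the dates from the MarketScan inpatient table, which is already a source for costs.

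Report the two versions side by side. They correspond to the two refill behaviours: the stated PDC is free of this artefact when refills keep to schedule, the adjusted one when supply is saved. State in advance that an adherence effect on costs, or a percentage mediated, will be claimed only if both agree, for example in sign and in whether the bootstrap interval excludes zero.

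The cost is a second PDC program and a second run of the mediation. The adjusted version overstates PDC in admitted patients whose refills stayed on schedule. Agreement would settle only the hospital-stay question. The link between fills and pharmacy cost remains: with the assumed $40 per covered day, the adjusted slope was still +6.1% and +3.7% in the two scenarios run.
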